4.2.7.5 Smoking status

Smoking status changes will be summarised by treatment group and visit for subjects in the safety analysis set during on-study period. A shift table will be produced to display current, former smoker and missing. The shift tables will present baseline and last observation post-baseline value.

4.2.8 Pharmacokinetics and immunogenicity

4.2.8.1 Analysis of pharmacokinetics

PK variables will be summarised using pharmacokinetics (PK) analysis set as defined in Section 2.1.3.

Serum samples for PK are scheduled to be collected at weeks 0, 4, 12, 24, 36, 52, 64 and at the premature IP discontinuation visit, where appropriate. Data will be assigned to weeks based on the windows defined in Section 3.1.5.

The following criteria will also apply for data to be included in the summary table:

- Only pre-dose samples at Week 0.
- Only pre-dose samples at Weeks 4, 12, 24 and 36 that were also between ≥ 21 and ≤ 35 days post the previous dose.
- Only samples that were taken between ≥ 21 and ≤ 35 days post the previous dose for Week 52.
- All samples for Week 64 that were taken within the visit window defined in Section 3.1.5.

For descriptive statistics of tezepelumab concentrations:

- If, at a given time point, 50% or less of the concentrations are non-quantifiable (NQ), the geometric mean, coefficient of variation (CV), arithmetic mean, and SD will be calculated by substituting the lower limit of quantification (LLOQ) divided by 2 for values which are NQ.
- If more than 50%, but not all, of the concentrations are NQ, the geometric mean, CV, arithmetic mean, and SD will be reported as not calculable (NC).
- If all the concentrations are NQ, the geometric mean and arithmetic mean will be reported as NQ and the CV and SD as NC.
- The median, minimum and maximum will also be reported.

The LLOQ of tezepelumab in serum will be 0.010 $\mu\text{g/mL}$.

Observed serum concentrations of tezepelumab for each individual will be listed by visit to confirm tezepelumab administration.

The PK data may be merged with those from other clinical studies for a population-based meta-analysis. If performed, results of the meta-analysis will be presented in a separate pharmacometrics report outside of the CSR, and this is not considered further in this SAP.

4.2.8.2 Analysis of immunogenicity

All analyses of immunogenicity variables will be based on the safety analysis set as defined in Section 2.1.2.

The number and percentages of ADA-positive subjects at each visit will be summarised by treatment group during the on-study period. Descriptive statistics including number of subjects, Q1 median, Q3 and range of the actual ADA titres by treatment group and visit, where possible, will be provided.

The ADA status across the study for each subject will also be classified and summarised by treatment group. Specifically, the following ADA results will be evaluated as number and proportion of subjects in cohorts together with corresponding titre summaries. However, if the number of ADA positive subjects in the safety analysis set is small, then the ADA variables may be listed only in the CSR:

- Subjects who are ADA positive at any time including baseline (ADA prevalence).
- Subjects who are baseline ADA positive.
- Subjects who are only baseline ADA positive.
- Subjects who are any post-baseline ADA positive.
- Subjects who are both ADA positive at baseline and positive in at least one post baseline measurement.
- Subjects who are ADA positive post-baseline and ADA negative at baseline (treatment-induced ADA).
- Subjects with treatment-boosted ADA, defined as baseline positive ADA titre that was boosted to a 4-fold or higher-level following IP administration.
- Subjects with treatment emergent ADA (ADA incidence): defined as the sum of treatment-induced ADA and treatment-boosted ADA.
- Subjects who are persistently positive; persistently positive is defined as at least 2 post-baseline ADA positive measurements (with ≥ 16 weeks between first and last positive) or an ADA positive result at the last available post-baseline assessment.
- Subjects who are transiently positive; transiently positive is defined as at least one post-baseline ADA positive measurement and not fulfilling the conditions for persistently positive.

For ADA summaries at a single time point (e.g. baseline ADA or by visit) the corresponding titre summary will be based on the titre of the positive sample for that particular visit. For proportions summarising across visits (e.g. any ADA post-baseline) the corresponding titre summaries will be based on the maximum titre of all positive samples for each subject.

Neutralizing ADA evaluations will be conducted on confirmed ADA positive samples. The test sample is deemed positive or negative for the presence of nAb to tezepelumab relative to a pre-determined (in assay validation) statistically derived cut point. The number and proportion of subjects who are nAb positive at any time will be evaluated.

The potential effects of ADA status and ADA titer on pharmacokinetics of tezepelumab will be evaluated. The potential association of immunogenicity with efficacy and safety may be evaluated, if appropriate.

5. INTERIM ANALYSES

A data cut off for an interim analysis to potentially stop the study due to futility of efficacy was originally planned to occur when 182 subjects had been randomised. As a result of the pause in recruitment due to COVID-19, the futility analysis is now planned to occur when approximately 30% of information has been achieved. An Independent Data Monitoring Committee (IDMC) will be used. Futility will be declared if the lower bound of an 80% confidence interval for the exacerbation rate ratio of tezepelumab vs. placebo is greater than 0.80. The futility boundary and method of assessing futility was chosen based on the operating characteristics of ~33% chance of stopping the study under the null hypothesis and ~4% chance of stopping the study assuming an exacerbation rate ratio of 0.70. Full details about the futility analysis decision rules and procedures will be specified in an IDMC charter, which will also specify the roles and responsibility of the IDMC members. Conducting the futility analysis results in power loss, but no alpha adjustment is required as there is no decision rule in place for stopping the study early to claim efficacy and no recovery of alpha from the futility analysis.

A data cut off for an interim analysis to inform sponsor Phase 3 planning will be conducted 1 month after Last Subject Randomised. The study will continue, even if sufficient efficacy is observed to inform an early go for planning purposes. The IDMC will be used and a blinding plan will be written to ensure that the study team, investigational site staff and subjects remain blinded to subject level treatment revealing data if an early planning decision is made. As the study will continue regardless, no adjustment to the type I error, alpha, is required.

6. CHANGE OF ANALYSIS FROM PROTOCOL

There are no changes of analysis from the protocol.

8. APPENDIX

8.1 Adverse events of special interest

8.1.1 Serious hypersensitivity reactions

Serious hypersensitivity reactions are defined as a combination of anaphylactic reactions (used with a time restriction) and events meeting regulatory serious criteria within the ‘Hypersensitivity’ narrow SMQ (no time restriction).

A subject will be considered to have this AESI if the subject has at least one adverse event with onset date during the relevant study period for analysis, which satisfies either of the following:

8.1.1.1 Anaphylactic reactions

- Potential anaphylactic reactions will be defined on the basis of Sampson’s criteria (see [Sampson et al., 2006](#)). These will be identified using a modified Standardised MedDRA Query (SMQ), with additional constraints on the timing of the AE onset date relative to the timing of the injection.
- Confirmed anaphylactic reactions will be those defined following medical review of the preferred terms identified as potential anaphylactic reactions, as well as any relevant supporting data.

8.1.1.2 Hypersensitivity

- Events meeting regulatory serious criteria within the ‘Hypersensitivity’ narrow SMQ.

AESIs and related definitions based on MedDRA terms are not included in this SAP to facilitate their maintenance (e.g. management of MedDRA version changes), and for convenience in using them directly in SAS programming. These detailed definitions will be finalised by the study team prior to primary DBL of the trial, and provided together with the study datasets at the time of submission.

8.1.2 Malignancy

Malignancy will be defined on the basis of an SMQ, using “SMQ: Malignant or unspecified tumors”.

AESIs and related definitions based on MedDRA terms are not included in this SAP to facilitate their maintenance (e.g. management of MedDRA version changes), and for convenience in using them directly in SAS programming. These detailed definitions will be finalised by the study team prior to primary DBL of the trial and provided together with the study datasets at the time of submission.

8.1.3 Helminth infections

Helminth infection will use an investigator-driven definition, i.e. will be directly determined from what is entered on the eCRF.

A subject will be considered to have this AESI if the subject has at least one preferred term where the dedicated Helminth Infection eCRF page was also completed for that event (linked by AE number), with AE onset date during the relevant study period for analysis.

8.1.4 Serious infections

Serious infections are defined as events meeting regulatory serious criteria within the ‘Infections and infestations’ SOC.

8.1.5 Guillain-Barre syndrome

Guillain-Barre syndrome will be defined using an SMQ.

AESIs and related definitions based on MedDRA terms are not included in this SAP to facilitate their maintenance (e.g. management of MedDRA version changes), and for convenience in using them directly in SAS programming. These detailed definitions will be finalised by the study team prior to primary DBL of the trial and provided together with the study datasets at the time of submission.

8.1.6 Serious cardiac events

Serious cardiac events are defined as events meeting regulatory serious criteria within the ‘Cardiac disorders’ SOC.

8.2 Accounting for missing data

Accounting for missing data for recurrent events (moderate/severe COPD exacerbation rate endpoint, severe COPD exacerbation rate endpoint)

In this study some subjects dropping out of the study potentially leads to unobserved events. The amount of missing data is minimised in this study as subjects are allowed in the protocol to switch to an alternative treatment or treatments after they discontinue from randomised treatment and are encouraged to complete visits until they withdraw from the study.

This section summarises how we will describe the pattern of and reasons for missing data from the study. It will also describe how we plan to account for missing data, including both the primary and

sensitivity analyses to assess the robustness of the treatment effect under different underlying assumptions to account for missing data.

Missing data descriptions

Tabular summaries for the percentage of subjects by the reason for discontinuation of randomised treatment as well as for withdrawal from the study will be presented by treatment group to describe why subjects discontinue from randomised treatment or withdraw from the study. The time to discontinuation of randomised treatment and withdrawal from the study will be presented using Kaplan Meier plots (overall and split by treatment related/not treatment related reason for withdrawal / IP discontinuation, as defined in Table 4 and Table 5 respectively). Dependent on these outputs additional exploratory analyses may be produced as deemed necessary to further understand the pattern of missing data.

Primary analysis under the primary estimand using the missing at random (MAR) assumption

The primary analysis for the primary endpoint of moderate to very severe COPD exacerbations allows for differences in outcomes over the study treatment period up to 52 weeks to reflect the effect of initially assigned randomised treatment as well as if subsequent treatments are taken. This primary analysis utilises all data over the 52-week period regardless of whether subjects remain on randomised treatment or whether they use an alternative biologic treatment. The primary analysis uses the negative binomial regression model with (logarithm of) the time at risk as an offset term and assumes that missing data are missing at random (MAR) and is a direct likelihood approach (DL).

Sensitivity analyses under the primary estimand using both MAR and missing not at random (MNAR) assumptions

To examine the sensitivity of the results of the primary analysis to departures from the underlying assumptions, additional analyses will be performed using controlled multiple imputation method introduced in [1] and further developed at AstraZeneca [2,3] which allows for different underlying assumptions to be used. As with the primary analysis, the sensitivity analyses include all data over the 52-week period regardless of whether subjects remain on randomised treatment or use an alternative biologic treatment.

For this method an underlying negative binomial stochastic process for the rate of exacerbations is assumed and post study withdrawal counts will be imputed conditional upon the observed number of events prior to the withdrawal. This allows various assumptions about the missing data to be analysed by modifying the post-withdrawal model assumption.

The method involves first fitting the primary analysis, i.e., negative binomial regression model to the observed data and then imputing post-withdrawal counts by sampling from the conditional negative binomial probability relating post-withdrawal counts and observed prior-withdrawal counts based on various assumptions.

$$\Pr(Y_{ij,2} = y_2 | Y_{ij,1} = y_1) = \frac{\Gamma(\gamma + y_1 + y_2)}{\Gamma(\gamma_2 + 1)\Gamma(\gamma + y_1)} p_j^{y_2} (1 - p_j)^{\gamma + y_1} \quad (1)$$

Here y_1 is number of counts before withdrawal from the study, y_2 is number of counts after withdrawal from the study, γ is the dispersion parameter and which is assumed to be the same for different treatment arms, j denotes the treatment arm and i denotes the subject identifier. Furthermore

$$p_j = \frac{p_{j,2} - p_{j,1} p_{j,2}}{1 - p_{j,1} p_{j,2}} \quad (2)$$

where $p_{j,1}$ is the negative binomial distribution (NBD) rate parameter before withdrawal from the study, and $p_{j,2}$ is the rate parameter after withdrawal from the study as determined based on various assumptions.

The imputed number of exacerbations that would have been seen is then combined with the observed exacerbations and data is analysed using the primary analysis methodology (DL). This analysis is repeated multiple times and the results combined using Rubin's formulae [7, 8].

The following default assumptions that may be used to impute the missing data for subjects who withdraw early from the study are as follows:

- a) MAR: Missing counts in each arm are imputed assuming the expected event rate within that arm.
- b) Dropout Reason-based Multiple Imputation (DRMI): Missing counts will be imputed differently depending on the reason for dropout; counts for subjects in the tezepelumab treatment arm who dropped out for a treatment related reason are imputed based on the expected event rate in placebo, whereas the remaining subjects who have dropped out are imputed assuming MAR. Treatment related reasons include (1) AEs, (2) Death and (3) development of study specified reasons to stop active treatments.

Some reasons for withdrawal are clearer to determine as treatment related (*Adverse Events, Death, Development of study-specific discontinuation criteria*) or non-treatment related (*Subject lost to follow up, eligibility criteria not fulfilled*). Other reasons are less clear such as site or study terminated by sponsor, subject decision and 'Other'; a review of each subject who withdraws from the study will therefore be carried out prior to unblinding the study. The review will include assessment of the reason for discontinuation of randomised treatment for those subjects who discontinued randomised treatment and then withdrew from the study and also free text for when the reason for withdrawal or discontinuation of randomised treatment is recorded as subject decision or other. Based on this review the default assumptions for DRMI as described in b) and Table 4 may be changed. A list of these subjects and the assumptions made under DRMI will be documented prior to unblinding of the study.

A summary of reasons for subjects withdrawing from the study and the corresponding arm used to calculate the imputed exacerbation rate under MAR and MNAR (DRMI) is given in Table 4.

Table 4 Reason for withdrawal

Reason for withdrawal	MAR	DRMI
Adverse Event	Tezepelumab	Placebo
Development of study-specific withdrawal criteria*	Tezepelumab	Placebo
Death	Tezepelumab	Placebo
Subject lost to follow up	Tezepelumab	Tezepelumab
Subject decision	Tezepelumab	Based on review prior to study unblinding
Site terminated by sponsor	Tezepelumab	Based on review prior to study unblinding
Study terminated by sponsor	Tezepelumab	Based on review prior to study unblinding
Physician decision	Tezepelumab	Based on review prior to study unblinding
Failure to meet randomisation criteria	Tezepelumab	Based on review prior to study unblinding
Other	Tezepelumab	Based on review prior to study unblinding

Note exacerbation rates for subjects in the placebo arm are imputed using the placebo arm rate

*Development of study-specific discontinuation criteria are based on the following: anaphylactic reaction to the IP requiring administration of epinephrine, development of helminth parasitic infestations requiring hospitalisation, a COPD-related event requiring mechanical ventilation; intensive care unit admission with intubation or extensive mechanical ventilation for a COPD related event

Together with the primary analysis, the sensitivity analyses are considered to cover the range from realistic to plausible worst-case assumptions about missing data. The MAR multiple imputation approach is expected to correspond closely to the primary analysis and is included to allow for comparisons with MNAR assumptions (specifically method b) using the same multiple imputation methodology.

The dropout reason-based multiple imputation (DRMI) approach was selected as the most conservative approach based on the fact that placebo subjects are receiving standard of care and are not expected to change to a substantially more effective treatment after withdrawing from study or study treatment. For subjects receiving tezepelumab who withdraw from the study due to treatment related reasons it is

assumed that at worst they would be on the standard of care treatment, i.e., the placebo arm. For subjects receiving tezepelumab who withdraw from the study due to non-treatment related reasons it seems reasonable to assume they would be similar to those subjects who complete treatment.

Sensitivity analysis under the supplemental estimand

The sensitivity analysis under the primary estimand using both MAR and MNAR (as described above) may be repeated under the supplemental estimand, where all available data will be included over the 52-weeks period until subjects discontinue randomised treatment or begin treatment with alternative biologic therapy, if the Kaplan-Meier plot split by treatment related/not treatment related reasons for IP discontinuation suggests any interesting patterns.

Imputation of missing counts up to Week 52 (including study withdrawal) will be performed for the primary endpoint of moderate or severe COPD exacerbations and for the severe COPD exacerbations endpoint as described above. For subjects who begin treatment with an alternative biologic therapy, data will be imputed by assuming subjects received tezepelumab. For those who discontinue randomised treatment (and do not start on alternative biologic therapy) the appropriate treatment arm used to calculate the imputed exacerbation rate under MAR and DRMI are given in Table 5. As for subjects who withdraw from the study, a review of each subject who discontinued randomised treatment will be carried out prior to unblinding the study where the default assumptions for DRMI as described in Table 5 may be changed. Again, a list of these subjects and the assumptions made under DRMI will be documented prior to unblinding of the study.

Table 5 Reason for discontinuation of randomised treatment

Reason for discontinuation of randomised treatment	MAR	DRMI
Adverse Event	Tezepelumab	Placebo
Development of study-specific discontinuation criteria*	Tezepelumab	Placebo
Severe non-compliance to protocol	Tezepelumab	Placebo
Subject lost to follow up	Tezepelumab	Tezepelumab
Subject decision	Tezepelumab	Based on review prior to study unblinding
Other	Tezepelumab	Based on review prior to study unblinding

Note exacerbation rates for subjects in the placebo arm are imputed using the placebo arm rate

*Development of study-specific discontinuation criteria are based on the following: anaphylactic reaction to the IP requiring administration of epinephrine, development of helminth parasitic infestations requiring hospitalisation, a COPD-related event

requiring mechanical ventilation; intense care unit admission with intubation or extensive mechanical ventilation for a COPD related event

Overall summary of analyses to account for missing data

A summary of the analyses to be carried out under different missing data assumptions are described in **Error! Reference source not found.**

Table 6 Summary of analyses

Assumption	Primary and supplemental estimands		
		MAR	MNAR
	DL	MAR	DRMI
Exacerbation rate for imputation in Teze arm ^b	No explicit imputation ^a	Teze for all reasons for withdrawal	Placebo for AEs, Death, and development of study specified discontinuation criteria, otherwise Teze or based on review prior to study unblinding.
Default definition for $p_{j,1}$ and $p_{j,2}$ based on formula (2) ^c .		$p_{j,2} = p_{j,1}$ For all treatment arms j=T and P	$p_{T,2} = p_{P,1}$ $p_{P,2} = p_{P,1}$ for reasons above otherwise $p_{T,2} = p_{T,1}$

- ^a Implicitly assumes unobserved rate the same as observed
- ^b Exacerbation rates for all subjects in the placebo arm are imputed using the placebo arm rate (i.e., $p_{P,2} = p_{P,1}$)
- ^c Note can be over written by review prior to study unblinding

T Tezepelumab 420 mg; P Placebo

Forest plots will be used to show the primary analysis results along with the missing data sensitivity analysis results. The rate ratio of tezepelumab versus placebo and corresponding 90% CI will be displayed in the x-axis.

It is noted that if the primary analysis is statistically significant, it is not necessarily expected that all sensitivity analyses will also give statistically significant results. If the results of the sensitivity analyses provide reasonably similar estimates of the treatment effect to the primary analysis, this will be interpreted as providing assurance that neither the lost information nor the mechanisms which cause the data to be missing have an important effect on primary analysis conclusions. Based on these outputs and the drug’s mechanism of action, the plausibility of the assumptions we make about missing data in the different analyses will be considered and described in the clinical study report.

Accounting for missing data for continuous endpoints (FEV₁ and SGRQ total score)

Primary analysis using the MAR assumption

As for the primary variable, the primary analysis of the FEV₁ and SGRQ total score as secondary endpoints will handle intercurrent events as per the primary estimand. The MMRM used is a DL approach in each case, which is valid under the MAR assumption.

Sensitivity analysis using MNAR assumptions

Sensitivity analyses of the repeated measures analyses will be performed for the FEV₁ and SGRQ total score using controlled sequential multiple imputation methods based on pattern mixture models as described in [5].

The method is analogous to the multiple imputation of exacerbation events and the imputation process consists of a sequence of MI steps, where each step is intended to impute missing values at 1 time-point only. This model will assume that some pre-specified subset of subjects who withdraw from the study have correlations with future (unobserved) visits similar to subjects in the placebo arm. As for the exacerbation events, this allows us to assess various deviations from the MAR assumption.

The assumptions that will be used to impute the missing data who withdraw early are as follows:

- (a) MAR: Assumes that the trajectory for subjects who dropped out in each arm is similar to those observed in their own treatment arm
- (b) DRMI: Assumes that the trajectory for subjects in the tezepelumab treatment arm who dropped out for treatment related reasons (according to the same classification as for the DRMI analysis of the primary endpoint) is similar to that of the placebo subjects, whereas the remaining subjects who has dropped out are imputed assuming MAR.

Approach b) can be considered more conservative than the approach for the primary analysis because the assumptions mean that as soon as subjects withdraw for a treatment related reason, they begin to worsen immediately.

The MNAR imputation is achieved by only using appropriate data at each stage of the imputation. Imputation will be done in 2 steps, the non-monotone (intermediate) missing SGRQ total score and FEV₁ values will be imputed first [Markov chain Monte Carlo (MCMC) method is used to partially impute the data using SAS PROC MI] and then the missing value at each visit will be imputed using a sequential regression method (using MONOTONE REG option of SAS PROC MI).

For example, to impute missing values at time t for subjects in the tezepelumab treatment arm, that dropped out due to an AE, include only placebo observations up to and including time t, plus observations from subjects in the tezepelumab arm that dropped out due to an AE, up to and including time t-1. This is done for each visit, one at a time using observed data, and missings just imputed.

Placebo missing observations and tezepelumab observations that are not missing due to AEs are imputed assuming missing at random (MAR) and follow the pattern of observed placebo observations in each treatment arm respectively. 100 imputations will be carried out, and a seed of 407016 will be used for the monotone imputation step and a seed of 766275 will be used for the sequential regression imputation step. The analysis of each of the imputed datasets will be as described for the primary analysis in Section 4.2.5.5 and Section 4.2.5.6 and these will be combined using SAS procedure PROC MIANALYZE.

To avoid possible convergence issues when fitting MMRM models to 100 imputed datasets, the estimated unstructured covariance parameters from the first imputation where the model converges will be used as the starting values to fit the models for all imputed datasets.

Results for continuous endpoints will be presented as per the recurrent event sensitivity analyses.

References

4. The Panel on Handling Missing Data in Clinical Trials; National Research Council. *The Prevention and Treatment of Missing Data in Clinical Trials*. National Academies Press, 2010.
5. *Guideline on Missing Data in Confirmatory Clinical Trials* 2 July 2010
EMA/CPMP/EWP/1776/99 Rev. 1
6. AZ guidance (clinical OPI): *Guidance on Minimizing the Loss of Patient Data in AstraZeneca Clinical Trials*, ed 2.0. (LDMS_001_00102309)
7. Fleming, TR. Addressing Missing Data in Clinical Trials. *Ann. Intern. Med.* 2011;154:113-117.

9. Rubin DB. Multiple imputation for nonresponse in surveys. New York: John Wiley & Sons, Inc. 1987.

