7. DISCONTINUATION OF TREATMENT AND SUBJECT WITHDRAWAL

7.1 Discontinuation of Study Treatment

Note that discontinuation from IP does NOT mean complete withdrawal from the study.

Subject may be discontinued from IP in the following situations:

- Subject decision. The subject is at any time free to discontinue IP, without prejudice to further treatment
- An adverse event considered to jeopardise the safety of a subject participating in the study
- Pregnancy
- Severe non-compliance with the Clinical Study Protocol
- Lost to follow up
- Development of any study specific criteria for discontinuation, including:
 - An anaphylactic reaction to the IP requiring administration of epinephrine
 - A helminth parasitic infestation requiring hospitalization
 - Intensive care unit admission with intubation or extensive mechanical ventilation for a COPD related event
- Any malignancy, except subjects who develop basal cell carcinoma or localized squamous cell carcinoma of the skin, provided that the malignancy has been excised and determined to have clear margins
- Development of one or more of the following:
 - Confirmed ALT or AST increase of ≥8 x ULN
 - Confirmed ALT or AST increase of ≥ 5 x ULN for more than 2 weeks
 - Confirmed ALT or AST increase of ≥3 x ULN and total bilirubin of ≥2 x ULN
 - ALT or AST of ≥3 x ULN with the appearance of fatigue, nausea, vomiting, right upper quadrant pain or tenderness, fever, rash, and/or eosinophilia (≥5% based on local laboratory results)

• Other reasons

Before a decision to discontinue a subject from IP is instituted, the AstraZeneca Study Physician should be consulted regardless of the reason for discontinuation.

See the SoA 1.1 for data to be collected at the time of IP discontinuation and follow-up and for any further evaluations that need to be completed.

If a subject discontinues IP due to a study specific discontinuation criterion, this should always be recorded as 'Development of study specific withdrawal' on the Discontinuation of Investigation Product form in the eCRF.

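### One sentence in SAP Appendix 8.2 tells the programmer to impute FEV1 and SGRQ in a way that contradicts the SAP's own definition of the drop-out reason-based analysis

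*SAP*

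**What the plan says.** All of this is in SAP Appendix 8.2, mainly in the part on continuous endpoints (FEV1 and SGRQ total score).

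- **MAR, assumption (a):** "Assumes that the trajectory for subjects who dropped out in each arm is similar to those observed in their own treatment arm".
- **DRMI, assumption (b):** placebo-like trajectories are for tezepelumab subjects who "dropped out for treatment related reasons (according to the same classification as for the DRMI analysis of the primary endpoint"). For everyone else: "whereas the remaining subjects who has dropped out are imputed assuming MAR".
- **The classification borrowed from the primary endpoint:** "Treatment related reasons include (1) AEs, (2) Death and (3) development of study specified reasons to stop active treatments". Table 4 lists adverse event, death and study-specific criteria as separate withdrawal reasons, each sent to placebo under DRMI. Several other reasons are left to a review before unblinding. Table 6 repeats this split.
- **Worked example of the imputation:** it covers tezepelumab subjects "that dropped out due to an AE, include only placebo observations up to and including time t".
- **Instruction for all other missing values:** placebo values, and tezepelumab values "not missing due to AEs are imputed assuming missing at random (MAR) and follow the pattern of observed placebo observations in each treatment arm respectively".

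The estimand table in SAP 8.3 describes the MAR sensitivity analyses of FEV1 and SGRQ as imputation from the same randomised arm.

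**The concern.** The last instruction is the one a programmer would code from, and it departs from the definition in two ways.

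1. **Donor data.** Values labelled MAR are said to follow placebo observations, but MAR is own-arm. The sentence also contradicts itself, because the tezepelumab arm contains no placebo observations. If every tezepelumab drop-out were imputed from placebo, the split by reason would disappear.
2. **Who is imputed from placebo.** The sentence divides AE from non-AE. Tezepelumab withdrawals for death, for study-specific criteria, or for a reason assigned to placebo at the pre-unblinding review would then be treated as MAR. The definition assigns them to placebo.

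DRMI is the plan's conservative check on these two secondary endpoints. The SAP fixes the number of imputations and the random seeds, yet its text can be built in three ways. A reader of the study report could not tell which was run.

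**Working it through.** There is no stated figure to reproduce. The check is textual, followed by an illustration of size.

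**Text, for a missing tezepelumab value in the DRMI analysis**

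| Withdrawal reason | Definition (b) with Table 4 | Instruction, literal | Instruction without the word placebo |
|---|---|---|---|
| Adverse event | placebo | placebo | placebo |
| Death | placebo | placebo | own arm |
| Study-specific criteria | placebo | placebo | own arm |
| Assigned to placebo at review | placebo | placebo | own arm |
| Lost to follow-up | own arm | placebo | own arm |

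Neither reading of the instruction reproduces the definition.

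**Size: inputs**

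- Visits (Protocol Table 2): SGRQ at weeks 0, 12, 24, 36, 48, 52; pre-bronchodilator FEV1 at weeks 0, 4, 12, 24, 40, 52.
- Drop-out m = 0.10. This is stated in SAP 1.3 for the exacerbation sample size, not for FEV1 or SGRQ.
- Assumed, in neither document: a constant treatment effect; drop-out spread evenly over visits; correlation rho^(gap in weeks/12) with rho 0.7 to 0.9; half of tezepelumab drop-outs treatment-related; 60% of those AEs.

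**Formula.** A drop-out with k observed post-baseline visits who is imputed from placebo keeps a share c_k of the effect. Here c_k is the sum of the regression coefficients of Week 52 on those k visits, with baseline also in the model. An own-arm imputation keeps all of it. So the share of the Week 52 difference kept = 1 − f × m′ × (1 − c), where f is the fraction of tezepelumab drop-outs imputed from placebo:

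- as defined: f = 0.5
- literal: f = 1
- AE-only: f = 0.5 × 0.6 = 0.3

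If subjects with no post-baseline value are left out, c is the mean over k = 1 to 4 and m′ = 0.8 × 0.10/(1 − 0.2 × 0.10) = 0.0816.

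**Example (SGRQ, rho 0.7).** c = (0.305 + 0.435 + 0.622 + 0.888)/4 = 0.562.

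- As defined: 1 − 0.5 × 0.0816 × 0.438 = 98.2%
- Literal: 1 − 0.0816 × 0.438 = 96.4%
- AE-only: 1 − 0.3 × 0.0816 × 0.438 = 98.9%

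**Results at 10% drop-out (rho 0.7 to 0.9)**

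| | c | As defined | Literal | AE-only |
|---|---|---|---|---|
| SGRQ | 0.562 to 0.830 | 98.2% to 99.3% | 96.4% to 98.6% | 98.9% to 99.6% |
| FEV1 | 0.420 to 0.760 | 97.6% to 99.0% | 95.3% to 98.0% | 98.6% to 99.4% |

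**Subjects with no post-baseline value.** SAP 4.2.5.5 requires one non-missing post-randomisation value for the repeated-measures model. The SAP does not say whether an imputed value satisfies this. If these subjects are included (c_0 = 0, m′ = 0.10) at rho 0.7:

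- SGRQ: c = 4 × 0.562/5 = 0.450, giving 97.25% as defined, 94.5% literal and 98.35% AE-only.
- FEV1: c = 4 × 0.420/5 = 0.336, giving 96.7%, 93.4% and 98.0%.

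**Other mixes of reasons.** Let the treatment-related share run from 25% to 75% and the AE share of those from 40% to 80%, again leaving out subjects with no post-baseline value. The literal reading is then 0.3 to 2.7 points (SGRQ) or 0.5 to 3.6 points (FEV1) below the definition. AE-only is 0.1 to 1.6 or 0.1 to 2.1 points above it.

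**Simulation under different assumptions.** Six visits, constant correlation 0.7, an effect rising to 0.30 SD, 10% drop-out, 200,000 per arm. With 50% of drop-outs treatment-related and 30% AEs, the final difference is 0.297 SD as defined, 0.287 literal and 0.300 AE-only. Over all mixes tried, the gaps from the definition run from about 0.003 to 0.013 SD. The ordering is the same throughout.

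**The case against.** The intended analysis is not in real doubt. Assumptions (a) and (b), Tables 4 and 6 and the estimand table agree with one another. The sentence itself names MAR and refers to each arm respectively, which points to own-arm donors. Since the tezepelumab arm has no placebo observations, the literal reading cannot strictly be programmed, and a careful programmer would probably recover the definition. The AE case above it is introduced as an example, so it is not a conflict by itself. AE in the next sentence may be shorthand for the reason-based split. All of this is fair and keeps the point small. It does not remove it: the sentence turns AE versus non-AE into the general rule, and Table 4 shows that AE does not cover the other treatment-related reasons.

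The SAP's rationale for DRMI also supports own-arm imputation: tezepelumab subjects who leave "due to non-treatment related reasons it seems reasonable to assume they would be similar to those subjects who complete treatment". That passage was written for exacerbations. It carries over only because the SAP calls the continuous method analogous, so it is supporting evidence and not the basis of the point.

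Stronger readings are tempting but unsupported:

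- **That the check is tilted towards tezepelumab.** The two slips pull in opposite directions, and the literal reading is the more conservative one.
- **That the main results are in doubt.** The sentence belongs to the account of the missing-not-at-random imputation for FEV1 and SGRQ. It does not govern the repeated-measures analyses, the MAR sensitivity analysis or any exacerbation analysis.
- **That Protocol 7.1 proves an AE filter would miss study-specific cases.** It concerns the form for discontinuing investigational product, whereas this analysis concerns withdrawal from the study. Table 4 is the relevant source.

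**Conclusion.** The contradiction is real and sits in current analysis text. Followed as written, the instruction builds a different analysis from the one the SAP defines.

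Its effect is small. In the base case at 10% drop-out, each reading differs from DRMI as defined by about 0.3 to 3 percentage points of the treatment difference. The largest simulated gap, 0.013 SD on a 0.30 SD effect, is about 4%. These sizes rest on assumed reason mixes, correlations and effect shapes, on a drop-out figure borrowed from the exacerbation sample size, and on the unsettled handling of subjects with no post-baseline value. They show order of magnitude only.

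Nothing confirmatory depends on it. P-values beyond the primary endpoint are nominal (SAP 4.1.2), and Appendix 8.2 judges sensitivity results by whether the estimates are similar. It should still be corrected, because the text currently allows three constructions of an analysis meant to be fixed in advance.

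**What to change.** Before unblinding, in the continuous-endpoint part of SAP Appendix 8.2:

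1. Replace the sentence on the remaining missing values with: *Placebo missing values, and tezepelumab values missing for reasons not classified as treatment-related (Table 4, as finalised at the pre-unblinding review), are imputed under MAR from observed values in the subject's own randomised arm.*
2. In the worked example just before it, replace the references to dropping out because of an AE with *for a treatment-related reason*.

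The cost is wording in two adjacent paragraphs. No new analysis or data are needed, and both edits only restore the SAP's own definition.
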